8. SAFETY EVALUATION

8.1 Overview of Safety Analysis Methods

All safety analyses will be performed using the safety population and summarized by actual treatment (MS1819-SD regardless of period vs. PERT regardless of period) allowing direct intrasubject comparison of the tolerability of MS1819-SD vs. PERT. Safety measures summarized will include AEs, laboratory data, vital signs, and concomitant medications. Additionally, exposure to study treatment during the study will be displayed.

Safety data will not be imputed, except for partial and missing dates, which will be imputed only for defining treatment-emergent AEs (TEAEs) and concomitant medications. Imputed dates will not be presented in data listings.

TEAEs will be defined as any AEs that occur or are reported to worsen in severity on or after the date of first dose of study treatment in period 1. Partial dates will be imputed for the purposes of defining TEAEs as follows:

- For a missing start day where the month and year are present, the start day will be set to the first day of the month, unless 1) the first day of the month is before the date of first dose of study treatment and the month and year are the same as the month and year of the date of first dose of study treatment, and 2) the end date is on or after the date of first dose of study treatment or the end date is completely missing, in which case the start day will be set to the first day of first dose of study treatment.
- For a missing start day and month where the year is present, the start day and month will be set to January 1st, unless 1) January 1st is before the date of first dose of study treatment and the year is the same as the year of the date of first dose of study treatment, and 2) the end date is on or after the date of first dose of study treatment or the end date is completely missing, in which case the start day and month will be set to that of the date of first dose of study treatment.
- For a missing end day where the month and year are present, the end day will be set to the last day of the month, unless the month and year are the same as the month and year of the last contact date for the subject, in which case the end day will be set to that of the subject's last contact date.
- For a missing end day and month where the year is present, the end day and month will be set to the subject's last contact date, unless the year of the subject's last contact date is greater than the end year, in which case the end day and month will be set to December 31st.

To categorize events with partial dates into their associated treatment periods, the imputation rules above will be defined relative to the first dose of the treatment period of interest separately. Thus, in the aforementioned rules, 'study treatment' refers to the treatment in the specified treatment period. Per the imputation rules, events with partial dates may require two imputed start dates to account for each treatment period. For example, an event with missing start day where the start month is the same as the

treatment start month for both study treatments will have the start date imputed to both the treatment start date of the first study period and the treatment start date of the second study period.

Partial and completely missing dates will be imputed for the purposes of classifying concomitant medications as follows:

- Partial dates will be imputed following the same algorithm as above for TEAEs.
- For a missing start date (i.e., day, month, and year are missing), the start date will be set to the date of first dose of study treatment for each period unless the stop date is prior the date of first dose of study treatment for a given period, in which case the start date will be set to the stop date.
- For a missing stop date (i.e., day, month, and year are missing), the medication will be treated as ongoing.

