## 7. INVESTIGATIONAL PLAN

### 7.1 Overall Study Design and Plan: Description

The OPTION study is a Phase 2, open-label, multicenter, 2x2 crossover trial to assess the safety and efficacy of MS1819-SD in patients with EPI due to CF in male and female patients aged 18 years or older. Efficacy will be evaluated by comparing treatment with MS1819-SD to treatment with porcine PERT. Refer to [Figure 1](#) for a flow chart of the study design.

During the treatment period, patients will be randomized to either MS1819-SD (2240 mg/day) or to their prestudy porcine PERT.

A Data and Safety Monitoring Board (DSMB), consisting of members external to AzurRx BioPharma, Inc., and including members of the Cystic Fibrosis Foundation Therapeutics, Inc. (CFFT) DSMB, will monitor safety throughout the trial. After the study is complete, the DSMB will review the efficacy/safety data.

Dosages will typically be fractionated as follows: 1/4 of the daily dose at each 3 main meals, and 1/8 at each of the 2 snacks (ie, 2240 mg/day will be fractionated as follows: 4 capsules of 140 mg with the morning, noontime, and evening meals, plus 2 capsules of 140 mg with the morning and evening snacks). Individual variations may occur as long as total daily dose is achieved.

The dose of prestudy porcine PERT will be the same dose that was being administered during the prestudy period.

The study will not employ a washout period between the first treatment period and the second treatment period. Recent experience with crossover lipase enzyme treatment from commercial PERTs to investigational lipase has demonstrated that symptoms of malabsorption may become evident within a matter of days, indicating little residual carryover effect of the original lipase (clintrials.gov NCT 02279498; clintrials.gov NCT0305140). Furthermore, the 3-week duration of treatment with either study agent is well established as sufficient to show the degree of lipase effectiveness (FDA Package Insert, CREON; FDA Package insert, PANCREAZE).

[figure not shown]
This study is divided into 4 main periods.

- Screening Period (up to 21 days)
- First Treatment Period (approximately 3 weeks) of the crossover design
- Second Treatment Period (approximately 3 weeks) of the crossover design
- End-of-Study/Early Withdrawal (approximately 2 weeks)

Refer to [Section 7.1.1 \(Table 1\)](#) for the Schedule of Assessments.

Figure 1: OPTION Study Design Flow Chart

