### 7.2.3 Safety Endpoints

AEs, SAEs and drop outs.

In addition, laboratory test results will be summarized ([Section 15.2](#)):

- Hematology
- Biochemistry
- Fasting lipid profile
- Urinalysis
- Serum MS1819 concentrations
- Antibodies against LIP2 lipase

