- Collect blood samples for vitamin determination (A, D, E, and K)
- Collect a serum sample for circulating anti-LIP2 lipase antibodies and MS1819-SD concentrations
- Record all fat, protein, and dose of study drug taken with every meal and snack during the confinement period

At the end of the supervised confinement (once the second blue dye marker sample has been collected), patients will crossover to their new treatment). Patients randomized to MS1819-SD will begin treatment on their prestudy porcine PERT. Patients randomized to their prestudy porcine PERT will begin treatment on MS1819-SD.

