### 8.3.3 Visit 10: End-of-Study /Early Withdrawal Visit (Day 56 ± 2)

Patients will return to the clinic for their End of Study visit approximately 2 weeks after their last dose of study drug (either MS1819-SD or the patient's prestudy porcine PERT). In the event that patients do not complete V9, an Early Withdrawal visit will be held approximately 2 weeks after the last dose of study drug (either MS1819-SD or the patient's prestudy porcine PERT). The procedures scheduled for the End-of-Study visit are the same as those that should be conducted for the Early Withdrawal visit. The following procedures will be performed at the End-of-Study/Early Withdrawal Visit:

- Focused physical exam to evaluate gastrointestinal tract, heart, and lungs
- Record any changes in AEs and concomitant medication
- Assess and record malabsorption signs and symptoms
- Collect a serum sample for circulating anti-LIP2 lipase antibodies and MS1819-SD concentrations
- Collect blood samples for vitamin determination (A, D, E, and K)

- Perform a urine pregnancy test (urine dip stick), if applicable

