In order to present summaries by treatment group regardless of sequence, the following parameters will be summarized as described below: safety laboratory, vital signs, signs and symptoms of malabsorption, weight, BMI, and serum liposoluble vitamins A, D, E, and K. These endpoints will be summarized relative to the time of first dose on a given study treatment. All post-randomization measurements will be relative to the time of the first dose. For example, in the MS1819 treatment column, the measurement at first dose will be Visit 3 if a subject is randomized to the MS1819-PERT sequence, and Visit 6 if a subject is randomized to the PERT-MS1819 sequence.

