8.5 Clinical Laboratory Evaluation

Values at Screening and at 3 weeks post first dose, as described in Section 3, for laboratory parameters for hematology and clinical chemistry will be summarized by treatment group for the safety population using descriptive statistics. Values at Screening, Visit 3 (At Randomization), At First Dose, and at 3 Weeks Post First Dose, as described in Section 3, for laboratory parameters for urinalysis will be summarized by treatment group for the safety population using descriptive statistics.

Shift tables based on classification of values with respect to the reference range will be summarized for the safety population for critical clinical chemistry and hematology laboratory tests by treatment group. Critical clinical chemistry and hematology laboratory tests are listed in the appendix for Table Display Specifications.

Post-baseline elevations in alanine aminotransferase (≥ 3 times the upper limit of normal [ULN]), aspartate aminotransferase (≥ 3 times ULN), total bilirubin (≥ 1.5 times ULN) will be summarized by treatment group at Screening and at 3 Weeks Post First Dose.

Hematology, clinical chemistry, hepatic monitoring, urinalysis, and pregnancy results will be presented in data listings for subjects in the safety population.

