Vitamin A, D, E, and K	X		X			X			X	X
Serum samples for anti-LIP2 lipase antibodies and MS1819-SD concentrations			X			X			X	X
Fecal pancreatic elastase ^j	X									
Diagnostic Test										
Spirometry	X									
Resume Prescribed PERT										
Switch back to prescribed porcine PERT ^k									X	

^A Screening procedures can occur up to 21 days before V1 through the first day of dosing (V3).

^B This first study telephone call will occur once eligibility for the patient is determined. Instructions on the randomization visit will also be communicated and patients will be told to bring in their prestudy porcine with them for V3.

^C Visits 4, 5, 7, and 8 are telephone visits to assess any changes to AEs and concomitant medications in addition to confirming the visit date for the next scheduled supervised confinement.

^D Visit 6 and Visit 9 are the first and second scheduled confinement visits and can take up to 7 days. A 7 day window is permitted around the scheduled confinement for both V6 and V9 to accommodate for scheduling. Patient should bring their prestudy porcine PERT to V3.

^E The Focused Physical Exam will evaluate gastrointestinal tract, heart, and lungs.

^F At the end of V6 (after the last stool sample has been collected), Patients that were randomized to MS1819-SD will begin treatment with their prestudy porcine PERT. Patients that were randomized to their prestudy porcine PERT will begin treatment with MS1819-SD.

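### The SAP specifies no analysis of the anti-LIP2 antibody endpoint, and its default by-treatment safety layout would place post-MS1819 samples under PERT

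*SAP*

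**What the plan says.** Protocol 7.2.3 lists the laboratory results to be summarized as safety endpoints, and "Antibodies against LIP2 lipase" is one of them. Serum is drawn at Visits 3, 6, 9 and 10 (Protocol 8.2.1, 8.2.3, 8.3.2 and 8.3.3). The Visit 6 instruction reads "Collect a serum sample for circulating anti-LIP2 lipase antibodies and MS1819-SD concentrations". Visit 10 comes after treatment ends: "Patients will return to the clinic for their End of Study visit approximately 2 weeks after their last dose of study drug".

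In the SAP the antibody appears only as a row of the schedule in 13.2, "Serum samples for anti-LIP2 lipase antibodies and MS1819-SD concentrations". SAP 8.5 describes summaries for hematology, clinical chemistry, urinalysis and liver-test elevations. Its listing sentence is "Hematology, clinical chemistry, hepatic monitoring, urinalysis, and pregnancy results will be presented in data listings for subjects in the safety population". Antibodies are in neither.

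Two general rules remain. SAP 8.1 states: "All safety analyses will be performed using the safety population and summarized by actual treatment (MS1819-SD regardless of period vs. PERT regardless of period", and it counts laboratory data among the measures covered. SAP 3 covers the safety laboratory parameters, presents them by treatment whatever the sequence, and adds: "These endpoints will be summarized relative to the time of first dose on a given study treatment".

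On design, Protocol 7.1 states: "The study will not employ a washout period between the first treatment period and the second treatment period". On departures from the protocol, SAP 11.1 records changes for stool weight and for malabsorption signs and symptoms only. Protocol 10.1 expects changes of analysis method to be described in the SAP and the study report.

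**The concern.** Most safety laboratory values describe the patient's current state, so a column for the treatment being taken is reasonable. An antibody against the study enzyme is different, because it records past exposure and may outlast it. Pooling by current treatment then mixes patients who have never received MS1819 with patients who have just finished three weeks of it.

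The protocol's case for omitting a washout rests on malabsorption symptoms returning within days and on lipase effect. It does not address an immune response.

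Safety and tolerability of 2240 mg/day is a primary objective. The product is a recombinant yeast lipase (Protocol 5.4), an immunoallergic reaction is a reason for withdrawal (Protocol 7.3.4), and this is the only antibody test collected. SAP 8.1 presents its layout as a within-patient comparison of tolerability. For antibodies, half of the PERT side would already have been exposed to MS1819.

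**Working it through.** The plan gives no antibody figure to reproduce. The check traces each sample through the stated rules and then counts.

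**Inputs.** At least 30 completers, at least 15 per sequence (SAP 2.2); about 38 enrolled, so 38/2 = 19 per sequence (Protocol 7.3.1, 1:1 allocation); two periods of about 3 weeks; Visit 10 about 2 weeks after the last dose.

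**Step 1: nominal time since the first MS1819 dose, and the slot under SAP 8.1 and SAP 3.**

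| Sample | MS1819-PERT: weeks | Slot | PERT-MS1819: weeks | Slot |
|---|---|---|---|---|
| Visit 3 | 0 | MS1819, at first dose | -3 | PERT, at first dose |
| Visit 6 | 3 | MS1819, 3 weeks; also PERT, at first dose | 0 | PERT, 3 weeks; also MS1819, at first dose |
| Visit 9 | 6 | PERT, 3 weeks | 3 | MS1819, 3 weeks |
| Visit 10 | 8 | none assigned | 5 | none assigned |

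**Step 2: make-up of the PERT column at 3 weeks.** It combines Visit 6 of PERT-MS1819 (15 completers, never exposed) with Visit 9 of MS1819-PERT (15 completers, exposed). The exposed share is 15/(15 + 15) = 50%. With all 38 patients it is 19/38 = 50%.

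**Step 3: what the columns would show.** Let p be the share positive after 3 weeks of MS1819, and q the share of those still positive at Visit 9. Both are assumed, as is no positivity without MS1819 exposure.

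- MS1819 column: p.
- PERT column: (15 × 0 + 15 × p × q)/30 = pq/2.
- PERT column as a fraction of the MS1819 column: (pq/2)/p = q/2, whatever p is.

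| q | PERT column as a fraction of the MS1819 rate | Example with p = 20% (MS1819 column 6 of 30) |
|---|---|---|
| 0 | 0 | PERT 0% |
| 0.5 | 0.25 | PERT 5% (1.5 expected of 30) |
| 0.8 | 0.40 | PERT 8% (2.4 expected of 30) |
| 1 | 0.50 | PERT 10% (3 of 30) |

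**Step 4: could the first-dose value correct this?** In MS1819-PERT, the at-first-dose value for PERT is Visit 6, after three weeks of MS1819. It could show that positivity came before PERT, but only if read patient by patient. No antibody shift or change from that visit is planned.

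**Step 5: effect of a sequence-based layout.** Taking Visit 9 of MS1819-PERT out of the PERT reference reduces its expected drug-induced rate from pq/2 to 0. The unexposed reference is then Visits 3 to 6 of PERT-MS1819, with 15 to 19 patients.

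**The case against.** The strongest reply is that the SAP contains no antibody table, so nothing has been misattributed. That is correct as far as it goes. A reader might infer that the SAP already counts MS1819 antibodies under PERT. It does not: this happens only if the protocol-required summary is produced under the general rules. If no summary is produced, the defect is an omission that SAP 11.1 does not record. Either way a correction is needed.

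Second, section 8 of the SAP does not use treatment-only columns throughout. Exposure is by treatment within period (8.2), events after the last period have a follow-up class (8.3), and prior medications are by planned sequence (8.6.3.1). The display specifications, which are not among the documents, could do the same for antibodies. But those exceptions are written out in the SAP and none covers antibodies, while 8.1 is worded to cover every safety analysis.

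Three stronger readings should be resisted:

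- *SAP 8.5 excludes Visit 10.* Its time points are set for tests that are not drawn at Visit 10, so they say nothing about antibodies. What stands is that Visit 10 has no assigned place.
- *The table would understate the MS1819 response.* In the model above the MS1819 column shows p, undistorted. The error is in the PERT column and in any comparison with it.
- *Clinical reactions would be missed.* An immunoallergic reaction would be recorded as an adverse event, with relatedness scored to each treatment, and the DSMB chair receives SAE reports in real time. No decision rule in either document uses antibody status.

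The zero-background assumption is also open to challenge. Protocol 5.4 notes that the source yeast occurs in ordinary foods, so some positivity before exposure is possible.

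**Conclusion.** The point holds in conditional form. The text establishes that a protocol safety endpoint has no analysis in the SAP and no recorded removal. It also establishes that the general rules would place half of the end-of-PERT antibody samples (15 of 30 completers) after MS1819 exposure, without a washout.

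How much this would distort a table is not established. The PERT column would show q/2 of the MS1819 rate, anywhere from none to one half, assuming equal sequences and no background positivity. The documents give neither seroconversion nor persistence, so no value of q can be preferred.

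The analysis is descriptive and the primary CFA comparison is unaffected. The point still merits correction before results are seen, because choosing columns or a baseline afterwards would be data-driven.

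**What to change.** 1. In SAP 8.1, exempt anti-LIP2 antibodies from the rule that summarizes by actual treatment regardless of period.
2. In SAP 8.5, tabulate and list them by sequence and visit (3, 6, 9 and 10) in the safety population. Take the last sample before the first MS1819 dose as baseline: Visit 3 for MS1819-PERT, Visit 6 for PERT-MS1819.
3. Attribute any new positive after that baseline to MS1819 exposure, including at Visit 10. Report separately any baseline-positive patient whose titre rises, if titres are measured.
4. Use Visits 3 to 6 of PERT-MS1819 as the unexposed reference, which also shows any background positivity.
5. If the endpoint will not be analyzed, record that in SAP 11.1.

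The cost is one exception clause, one descriptive table and one listing, from samples already planned. With only 15 to 19 patients per sequence the table will be imprecise and should stay descriptive.

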4.3 Safety Population

The safety population, which will be used for all safety analyses unless stated otherwise, will include all randomized subjects who receive at least 1 dose of treatment. Subjects in the safety population will be analyzed according to the actual treatment received regardless of their randomized assignment.

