TEAEs will be summarized for all subjects in the safety population. TEAEs will be summarized by treatment group. The total number of TEAEs occurring will be shown. The number and percentage of subjects experiencing any TEAE will also be provided. In addition, summary tables will reflect a count and percentage of subjects experiencing at least 1 TEAE in each system organ class and preferred term. All percentages will use the number of subjects in the safety population as the denominator. Therefore, if a subject has more than 1 AE within a system organ class, the subject will be counted only once in that system organ class. If a subject has more than 1 AE that codes to the same preferred term, the subject will be counted only once for that preferred term. Tabular summaries will be sorted by descending frequency by system organ class and by preferred term in the MS1819 treatment group.

Treatment-emergent AEs will be presented by treatment group and overall with percentages that use the number of subjects in the safety population as the denominator.

Treatment-emergent AEs will also be summarized by maximum relationship to study drug and maximum severity. Relationship to each study treatment (MS1819-SD and prestudy PERT) will be scored as Related or Unrelated. Severity will be rated as Mild, Moderate, or Severe. All percentages will use the number of safety subjects as the denominator. Summary tables will reflect a count and percentage of subjects experiencing at least 1 TEAE in each system organ class, preferred term and grouping, relationship, or severity. If a subject experiences more than 1 AE within a system organ class or preferred term, that subject will be counted only once for that event under the maximum severity or most related category for the study drug. Similarly, in the event that relationship or severity data are missing, the study analysis will follow the assumption of maximum relationship or severity in the summary tables. These summaries will be presented by treatment group and overall with percentages that use the number of subjects in the safety population as the denominator. The tabular summaries will be sorted by descending frequency by system organ class and by preferred term in the MS1819 treatment group.

All AEs will be presented in data listings for subjects in the safety population.

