8.4 Deaths, Serious Adverse Events, and Other Significant Adverse Events

Treatment-emergent SAEs, TEAEs leading to study discontinuation, TEAEs resulting in death, treatment-emergent SAEs by relatedness, treatment-emergent SAEs leading to discontinuation, and treatment-emergent SAEs resulting in death will be summarized for all subjects in the safety population. Summary tables will reflect a count and percentage of subjects experiencing at least 1 TEAE in each system organ class and preferred term within each AE subset (serious, leading to discontinuation, death). These summaries will be presented by treatment group and overall with percentages that use the number of subjects in the safety population as the denominator. These tabular summaries will be sorted by descending frequency by system organ class and by preferred term in the MS1819 treatment group.

Adverse events leading to study discontinuation, AEs resulting in death, and SAEs will be presented in data listings for subjects in the safety population.

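### SAP 8.1 promises a within-patient comparison of tolerability, but the SAP text plans no summary that gives it for patients who took both treatments

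*SAP*

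**What the plan says.** Safety against porcine PERT is part of the primary objective (SAP 2.1.1), and SAP 2.6 says the sample size was chosen mainly for safety. SAP 8.1 pools each treatment over periods, "allowing direct intrasubject comparison of the tolerability of MS1819-SD vs. PERT".

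The planned output is in SAP 8.3 and 8.4:

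- "TEAEs will be summarized by treatment group", and "summary tables will reflect a count and percentage of subjects experiencing at least 1 TEAE in each system organ class and preferred term".
- There is also an overall column: "Treatment-emergent AEs will be presented by treatment group and overall with percentages". For serious events, discontinuations and deaths, "These summaries will be presented by treatment group and overall".
- "All percentages will use the number of subjects in the safety population as the denominator". That population "will include all randomized subjects who receive at least 1 dose of treatment" (SAP 4.3), so it includes patients who took only one of the two treatments.
- "All AEs will be presented in data listings for subjects in the safety population".

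SAP 8.3 assigns each TEAE to period 1, period 2 or both, and puts events after a patient's last period into a separate follow-up class. It does not say which column of the tables that class enters. Protocol 10.6 limits the safety analysis to descriptive methods.

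**The concern.** In a crossover each patient is his or her own control. The tolerability comparison therefore rests on four groups: patients with the event on MS1819 only, on PERT only, on both, and on neither. The SAP text plans no table of these groups and no paired difference with an interval.

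Two things are at stake. The first is precision: a reader who treats the two columns as independent groups will get an interval that is too wide when the same patients tend to have events on both treatments, and too narrow when different patients do. The second is composition: the columns mix patients who took both treatments with patients who took one, and only the former can contribute to a comparison within patients.

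The number of patients with events on both treatments also depends partly on the SAP's own rules. An event occurring in both periods is attributed to both (SAP 8.3), and an event with a partial date may be given a start date in each period (SAP 8.1).

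**Working it through.** **The plan's own safety figure.** SAP 2.6 gives 0% to 10% as the 95% CI for an event not seen in 30 completers. The rule of three gives 3/30 = 10.0%, and the one-sided exact limit is 1 - 0.05^(1/30) = 9.5%, so the figure reproduces. (The two-sided exact limit is 1 - 0.025^(1/30) = 11.6%.) This figure concerns one rate, not a comparison. The plan gives no precision for MS1819 against PERT.

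**Inputs.** n = 30 patients on both treatments is the SAP's planned number of completers. The documents give no adverse event rates, so 12 patients with a TEAE on MS1819 and 6 on PERT are assumed.

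**What the treatment columns fix.** Let a = event on both, b = MS1819 only, c = PERT only. Then b = 12 - a and c = 6 - a, so b - c = 6 whatever a is. The paired difference is always 6/30 = 20 points. Over all 465 unequal pairs of counts with n = 30, no overlap changes the sign.

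**What they leave open.** The Wald standard error is SE = sqrt(b + c - (b - c)²/n)/n, with (b - c)²/n = 36/30 = 1.2.

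| Overlap a | b, c | SE | 95% CI (points) | Overall, a + b + c |
|---|---|---|---|---|
| 6 | 6, 0 | sqrt(4.8)/30 = 0.073 | 5.7 to 34.3 | 12 |
| 3 | 9, 3 | sqrt(10.8)/30 = 0.110 | -1.5 to 41.5 | 15 |
| 0 | 12, 6 | sqrt(16.8)/30 = 0.137 | -6.8 to 46.8 | 18 |

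Treating the columns as independent groups gives SE = sqrt(0.4×0.6/30 + 0.2×0.8/30) = 0.115 and a CI of about -2.6 to 42.6, whichever row is true.

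**What the overall column adds.** If it counts unique subjects with an event on either treatment, then a = n(MS1819) + n(PERT) - n(overall): 12 + 6 - 12 = 6, or 12 + 6 - 18 = 0. The rows of the table can then be told apart.

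**Where that stops working.**

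1. Follow-up TEAEs. Suppose the true overlap is 6 (overall 12), and three further patients have only a follow-up event that enters the overall column (an assumption). Overall becomes 15, and subtraction gives 12 + 6 - 15 = 3: the reader takes the second row when the first is true.
2. One-period patients. The SAP plans for 20% dropout: 30/0.8 = 37.5, hence 38. Suppose 38 are treated and 8 of them took MS1819 only (an assumption, and an extreme one). The table shows 12/38 against 6/38, a difference of 15.8 points. If k of the 12 are one-period patients, the counts among those who took both are 12 - k against 6. At k = 7 this is 5 against 6, or -1/30 = -3.3 points; at k = 8 it is 4 against 6, or -6.7 points. Subtraction does not help, because one-period patients stay inside the MS1819-only group.

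**The case against.** The case on the other side is substantial.

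- The tables are not by treatment alone. The overall column separates overlap 6 from overlap 0 (12 subjects against 18), so a reader who infers that the planned tables would look identical in the two scenarios is mistaken. Subjects are counted once per term, so unique subjects is the natural reading of that column. This stands, subject to the two limits worked out above.
- A reader might infer that the same counts allow opposite conclusions about tolerability. For patients who took both treatments they do not: direction and size are fixed and only precision varies. A change of direction needs one-period patients, and in the example needs at least 7 of 8 of them to have had an event.
- A reader might add a test. Exact McNemar gives p = 0.031 at overlap 6 and p = 0.238 at overlap 0. The plan makes no such test and describes safety only, so no conclusion that it would draw is overturned.
- The pairing is not thrown away. Events are assigned to periods, all AEs are listed, and SAP 8.2 lists first and last dose times by period. The within-patient table could be built by hand from these. This stands, but a listing is not a summary.
- SAP 8.1 could mean no more than that the same subjects feed both columns. That reading is possible, but the sentence speaks of a direct intrasubject comparison.
- SAP 1 and 14 place table layouts in a separate document that was not available. A paired layout may be there.

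**Conclusion.** The point holds as a moderate reporting gap. SAP 8.1 names a within-patient comparison on a primary objective, and the SAP text specifies no summary that delivers it for patients who took both treatments. In the illustration the same two treatment columns fit a 20-point difference with a 95% CI of 6 to 34 or of -7 to 47. The overall column resolves this only under conditions that the SAP does not state, and neither it nor the treatment columns separate one-period patients.

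The size rests on assumed counts (12 and 6 in 30), on the two extreme overlaps, and on a Wald interval, which is weak at n = 30 with an empty cell; it shows scale and does not predict the result. The possible change of direction rests on a further assumption about dropouts. The trial's validity and the planned descriptive analysis are not in question.

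**What to change.** Add one descriptive table to SAP 8.3, restricted to patients who received at least one dose of each treatment:

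- Number and percentage with the event on MS1819 only, PERT only, both and neither, overall and by sequence.
- The paired difference with a 95% CI suited to small paired samples (for example Tango's score interval or Newcombe's paired interval), and no test.
- Rows for any TEAE, related TEAE, severe TEAE, SAE and the gastrointestinal system organ class.
- Follow-up TEAEs excluded, and this stated in the table's definition.

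Keep the present tables. If the Table Display Specifications already contain such a layout, a sentence in SAP 8.3 pointing to it is enough.

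The cost is one extra table from data already collected, with no change to trial conduct.
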